Bullous dermatitis	Hold study treatment. Grade 1-2 bullous dermatitis: discussion with the Novartis Medical Monitor is required before considering resuming study treatment. Grade 3 bullous dermatitis: consider resuming therapy after expert consultation and documented discussion with the Novartis medical monitor. Grade 4 bullous dermatitis: discontinue study treatment.
Stevens-Johnson syndrome (SJS), or Lyell syndrome/toxic epidermal necrolysis (TEN)	Permanently discontinue study treatment.
Hematology	
Neutropenia (ANC)	
Grade 3 or Grade 4	Hold study treatment. Upon resolution to \leq Grade 2 or baseline within \leq 7 days, resume study treatment without dose modification, after discussion with the Novartis Medical Monitor.
Febrile neutropenia	
Grade 3 or Grade 4	Hold study treatment. Upon resolution of fever and improvement of neutropenia to \leq Grade 2 or baseline, resume study treatment without dose modification, after discussion with the Novartis Medical Monitor.
Thrombocytopenia	

Worst toxicity CTCAE^a grade	Recommended Dose Modification
Grade 3	Hold study treatment. Upon resolution to \leq Grade 2 or baseline, resume study treatment without dose modification. For Grade 3 associated with major bleeding, discontinue study treatment.
Grade 4	Discontinue study treatment.
Anemia	
Grade 3 or Grade 4	Hold study treatment. Upon resolution to \leq Grade 2 or baseline within \leq 7 days, resume study treatment without dose modification.
Lymphopenia	
Any grade	Treatment-related lymphopenia does not require study treatment hold or discontinuation.
Other laboratory adverse events, not specified elsewhere in table and not included in the consensus guidelines	
Grade 3	Hold study treatment. Upon resolution to \leq Grade 1, resume study treatment without dose modification.
Grade 4	Isolated Grade 4 electrolyte abnormalities not associated with clinical sequelae and corrected after appropriate management within 72 hours of their onset do not require discontinuation. In the case of Grade 4 electrolyte imbalances associated with clinical sequelae, or not resolved to \leq Grade 1 within 72 hours despite appropriate management, discontinue study treatment.

Worst toxicity CTCAE^a grade	Recommended Dose Modification
Other non-laboratory adverse events, not specified elsewhere in table and not included in the consensus guidelines	
Grade 2	Consider study treatment hold, at Investigator discretion. Upon resolution to ≤ Grade 1, resume study treatment without dose modification.
Grade 3	Hold study treatment. Upon resolution to ≤ Grade 1, resuming study treatment must be discussed with the Novartis Medical Monitor.
Grade 4	Discontinue study treatment.

All dose modifications should be based on the worst preceding toxicity.

^a Common Toxicity Criteria for Adverse Events (CTCAE)

*Note: anti-diarrheal medication is recommended at the first sign of abdominal cramping, loose stools or overt diarrhea.

**Note: If Grade 3 or 4 hyper-bilirubinemia is due to the indirect (non-conjugated) component only, and hemolysis as the etiology has been ruled out as per institutional guidelines (e.g., review of peripheral blood smear and haptoglobin determination), then delay study treatment until resolved ≤ Grade 1, and resume study treatment at the discretion of the investigator.

***Note: A CT scan or other imaging study to assess the pancreas, liver, and gallbladder must be performed within one week of the first occurrence of any ≥ Grade 3 of amylase and/or lipase.

[figure not shown]
[figure not shown]

Table 6-3 Criteria for defining dose limiting toxicities for the Japanese safety run-in part

For the purpose of Japanese safety run-in part, DLT defined as follows: Any Grade 4 AEs are DLTs with the exception of:
Neutropenia lasting \leq 5 days that is not associated with fever or other clinical symptoms. Lymphopenia or Leukopenia. Electrolyte abnormalities that are not associated with clinical sequelae or deemed to be not clinically significant and are corrected with appropriate management or supplementation within 72 hours of the onset.
Any Grade 3 AEs are DLTs with the exception of:
Infusion reaction that resolves to \leq Grade 1 within 6 hours. Nausea and vomiting that resolves within 2 days after starting optimal anti-emetic therapy. Thrombocytopenia without significant bleeding. Anemia grade 3 that resolves within 7 days in the absence of transfusion Diarrhea that resolves within 2 days after starting optimal anti-diarrhea treatment. Hypertension that resolves within 7 days after starting treatment. Infection or fever in the absence of neutropenia that resolves within < 5 days. Rash or photosensitivity that resolves within 7 days after starting treatment. Fatigue that resolves within 7 days. Immune-related adverse events that resolve within 7 days after starting treatment with corticosteroids.
The following Grade 2 AEs are considered DLTs:
Newly emerging total bilirubin \geq 2 x ULN with \geq CTCAE Grade 3 AST/ALT. Pneumonitis that does not resolve within 7 days after starting treatment with corticosteroids. Eye pain or reduction of visual acuity that does not respond to topical therapy and does not improve to Grade 1 severity within 2 weeks of the initiation of topical therapy OR requires systemic treatment. Other clinically significant toxicities, including a single event or multiple occurrences of the same event may be considered as DLTs.

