Non-immune related AEs (non-irAEs), resulting in dose delay of PDR001 or NIR178 lasting longer than 14 days will necessitate discontinuation of study drug. Exceptions may be made if the Investigator considers it to be in the patient's best interest to resume therapy, following documented discussion with Novartis. In the event of immune related AEs (irAEs) requiring treatment interruption, combination therapy with NIR178 and PDR001 can resume only when the specific irAE has resolved as outlined in [Table 6-2](#), patient requires no more than physiologic dose of steroids (steroid equivalent of ≤ 10 mg/day of prednisone), and patient has discontinued any other immunosuppressive drugs that were initiated for the irAE. Overall, for irAEs that do not recover to \leq Grade 1 or baseline at a dose of immunosuppression of ≤ 10 mg/day prednisone or equivalent within 12 weeks after initiation of immunosuppressive therapy, and/or requiring continuation of other immunosuppressive drugs, PDR001 and NIR178 must be permanently discontinued ([Figure 6-1](#)).

Figure 6-1 Management of toxicity requiring dose interruptions

[figure not shown]
[figure not shown]

[figure not shown]
Table 6-2 Criteria for dose reduction / interruption and re-initiation of NIR178 and PDR001 treatment for adverse drug reactions

The instructions provided in this table and the criteria for dose reduction / interruption are used to determine a protocol deviation.

[figure not shown]
Worst toxicity CTCAE^a grade	Recommended Dose Modification
Infusion reaction or hypersensitivity reaction	
Grade 1	Decrease infusion rate until recovery of the symptoms.
Grade 2	Stop infusion immediately, and keep line open. Follow institutional guidelines for the management and follow-up of infusion reaction. Restart infusion at 50% of previous rate under continuous observation. Ensure that there is a minimum observation period of 1 hour prior to restarting the infusion. If the AE recurs at the reinitiated slow rate of infusion, and despite oral pre-medication, then permanently discontinue study treatment.
Grade 3 and Grade 4	Discontinue infusion immediately, and discontinue study treatment. Provide supplemental oxygen, fluids, and other resuscitative measures as needed. Monitor vital signs (e.g. blood pressure, pulse, respiration, and temperature) every 15 ± 5 minutes until resolution.
Cytokine Release Syndrome (CRS)	
Grade 2	See instructions for Grade 2 Infusion Reaction above.

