Grade 2	Hold study treatment. GI consultation. Upon resolution to ≤ Grade 1 and tapering of steroid requirement to ≤ 10 mg prednisone per day, resume study treatment without dose modification after discussion with the Novartis Medical Monitor.
Grade 3	Hold study treatment. GI consultation. Upon resolution to ≤ Grade 1 and tapering of steroid requirement to ≤ 10 mg prednisone per day, consider resuming study treatment after discussion with the Novartis Medical Monitor.
Grade 4	Discontinue study treatment.
AST and/or ALT elevation	
Grade 2 AST and/or ALT	Hold study treatment. Manage per institutional practice. Upon resolution to ≤ Grade 1 or baseline, consider resuming study treatment without dose modification. After resuming treatment with NIR178, close monitoring with at least weekly LFTs is recommended for 1 cycle of treatment. If suspicion of autoimmune hepatitis, the following confirmatory diagnostic serological markers are recommended: Serum autoantibodies including antinuclear (ANA), smooth muscle antibody (SMA) or antibody to liver-kidney microsomes (anti-LKM), Immunoglobulin levels, total globulins, and when possible liver biopsy.
Grade 3 AST and/or ALT ALT or AST >3 x ULN and TBL >2 x ULN (or international normalized ratio [INR] >1.5) ALT or AST >3 x ULN and symptoms of hepatitis (eg, fatigue, nausea, vomiting, right upper quadrant pain or tenderness, fever, rash, and/or eosinophilia [>5%])	Hold study treatment. Manage per institutional practices. Upon resolution to ≤ Grade 1 or baseline within 7 days, consider resuming PDR001 at the same dose and NIR178 at a lower dose after discussion with the Novartis Medical Monitor. After resuming treatment with NIR178, close monitoring with at least weekly LFTs is recommended for 1 cycle of treatment. Otherwise, discontinue study treatment. If suspicion of autoimmune hepatitis, the following confirmatory diagnostic serological markers are recommended: Serum autoantibodies including antinuclear (ANA), smooth muscle antibody (SMA) or antibody to liver-kidney microsomes (anti-LKM), Immunoglobulin levels, total globulins, and when possible liver biopsy.
Grade 4 AST and/or ALT	Discontinue study treatment.
Isolated total bilirubin elevation**	

[figure not shown]
Worst toxicity CTCAE ^a grade	Recommended Dose Modification
Grade 2	Hold study treatment. Upon resolution to ≤ Grade 1 or baseline, may continue study treatment without dose modification.

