Grade 3	Hold study treatment. Upon resolution to ≤ Grade 1 or baseline, may consider resuming study treatment after discussion with the Novartis Medical Monitor.
Grade 4	See footnote**. Otherwise, discontinue study treatment.
Combined elevations of AST or ALT and total bilirubin	

For participants with normal baseline ALT and AST and total bilirubin value: AST or ALT >3.0 x ULN combined with total bilirubin >2.0 x ULN without evidence of cholestasis OR [AST or ALT >3x baseline OR > 8.0 xULN], whichever is lower, combined with [total bilirubin >2x baseline AND >2.0 x ULN]
	
Mandatory: Interrupt treatment and adjudicate for DILI: Repeat as soon as possible, preferably within 48 hours from awareness of the abnormal results, then with weekly monitoring of LFTs, or as clinically indicated, until AST, ALT, or total bilirubin have resolved ≤ ULN or to baseline. (Refer to the Section 6.2.2.1 for additional follow-up evaluations as applicable.) If causality assessment indicates that DILI is probable: Permanently discontinue participant from treatment. If not DILI: Treat the identified cause according to institutional guidelines. Once resolved, reduce by one dose level.

**Note: For participants with Gilbert's syndrome, at least 2-fold increase in direct bilirubin.
	
Asymptomatic amylase and/or lipase elevation***	
Grade 3 or Grade 4, not associated with symptoms or clinical manifestations of pancreatitis***	
Continue study treatment. If levels do not resolve to ≤ Grade 2 within ≤ 14 days after the initial report, hold study treatment. Upon resolution to ≤ Grade 2, may resume study treatment without dose modification, after discussion with the Novartis Medical Monitor.

Pancreatitis	
Grade 2/ radiologic evidence	
Hold study treatment. Manage per institutional practice. Upon resolution to ≤ Grade 1, may resume study treatment without dose modification, if no clinical evidence of pancreatitis and after discussion with the Novartis Medical Monitor.

[figure not shown]
Worst toxicity CTCAE^a grade	Recommended Dose Modification
Grade 3 or Grade 4	Discontinue study treatment.
Renal	
Serum creatinine	
Grade 2	Hold study treatment. Manage per institutional practice. Upon resolution to ≤ Grade 1, may resume study treatment without dose modification after discussion with the Novartis Medical Monitor.
Grade 3 or 4	Discontinue study treatment.
Musculoskeletal	

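### Protocol Table 6-2 gives two unranked sets of resume-or-stop rules for one combined liver pattern in normal-baseline, non-cholestatic patients

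*Protocol*

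**What the plan says.** Table 6-2 in Protocol Section 6.2.1 sets the criteria for holding, reducing, resuming and stopping treatment. Its header says that its instructions and criteria "are used to determine a protocol deviation".

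**Grade 3 row of the AST/ALT block.** Besides Grade 3 AST or ALT, this row lists "ALT or AST >3 x ULN and TBL >2 x ULN (or international normalized ratio [INR] >1.5". It carries no condition on baseline values or cholestasis. Treatment is held. If values return to Grade 1 or lower, or to baseline, inside 7 days, the site may "consider resuming PDR001 at the same dose and NIR178 at a lower dose after discussion with the Novartis Medical Monitor". If that is not met: "Otherwise, discontinue study treatment". The cell does not make the outcome depend on a causality finding.

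**Combined-elevations row.** For participants with normal baseline ALT, AST and bilirubin, the trigger is "AST or ALT >3.0 x ULN combined with total bilirubin >2.0 x ULN without evidence of cholestasis". A second, baseline-relative trigger follows. Interruption and adjudication for DILI are mandatory. "If causality assessment indicates that DILI is probable: Permanently discontinue participant from treatment". If the cause is not DILI, that cause is treated and, once it has resolved, the dose is reduced by one level. There is no 7-day condition and no mention of the medical monitor. The only level of resolution stated is in the monitoring instruction: ULN or lower, or baseline.

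**The concern.** A combined rise in transaminases and bilirubin is the pattern that Section 6.2.2.1 treats as possibly severe DILI. Where one patient meets both rows, a site can follow one instruction faithfully and still be out of line with the other. Section 6.2.1 adds that departures from mandatory interruptions or reductions are not allowed, and the table is the yardstick for deviations.

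Three things are at stake: whether similar patients are managed alike, whether deviations can be classified consistently, and how the case enters the tables. SAP Section 2.3.2 tabulates and lists protocol deviations. SAP Sections 2.4.1.4 and 2.6.2.1 count dose reductions, permanent discontinuations and the adverse events behind them. Which row was followed decides whether a patient appears as a reduction or a discontinuation. The response-rate decision rules and the sample size are not in question.

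**Working it through.** The documents state no figure to reproduce. The check is whether the triggers overlap, and then what each row directs.

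**Overlap.** The enzyme and bilirubin thresholds are the same in both rows (3 and 2 times ULN). The combined row's matching trigger adds two conditions: normal baseline values and no evidence of cholestasis. A patient who satisfies both conditions and has the pattern therefore meets both rows. A cholestatic patient with normal baseline values meets only the Grade 3 row. Patients with elevated baseline values come under a different threshold (Section 6.2.2.1; second trigger in the combined row).

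**Directions for a patient meeting both rows.** Both begin by holding treatment. Crossing DILI probable (yes/no) with resolution within 7 days (yes/no) gives four cases:

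| Case | Grade 3 row | Combined-elevations row | Result |
|---|---|---|---|
| 1. DILI probable, resolved within 7 days | Resumption may be considered | Permanent discontinuation | Contrary |
| 2. DILI probable, not resolved within 7 days | Discontinue | Permanent discontinuation | Agree |
| 3. Not DILI, resolved within 7 days | Resumption may be considered, NIR178 lower | One-level reduction once resolved | Same direction, different conditions |
| 4. Not DILI, resolved after 7 days | Discontinue | One-level reduction once resolved | Contrary |

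The combined row speaks of reducing rather than resuming, but a reduction after resolution makes sense only if dosing restarts.

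In case 3 the conditions still differ. The Grade 3 row asks for Grade 1 or lower, or baseline, and for discussion with the medical monitor. The combined row's stated level is ULN or lower, or baseline, and it asks for no such discussion. It also does not name the drug to be reduced. Section 6.2.1 does not permit PDR001 reductions, so this can only mean NIR178.

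**Search for a ranking rule.**

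- The exception in Section 6.2.1 lets a patient who is benefiting continue after documented discussion with the sponsor. It does not say which row applies.
- The general delay limit for events that are not immune-related is 14 days, with exceptions. It does not match the 7 days, and it leaves days 8 to 14 as the interval in which case 4 is plainly contrary.
- The 12-week limit for immune-related events does not match the 7 days either.
- The footnote on worst preceding toxicity cannot choose between rows triggered by the same values.
- Section 6.2.2.1 repeats the thresholds for normal-baseline patients without the cholestasis condition. It sets out the work-up and the SAE reporting, not the rule for resuming or stopping.

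**The case against.** **The conflict is softer than a count of two in four suggests.** In case 1 the Grade 3 row only permits resumption to be considered, while the combined row is mandatory, so a site that stops complies with both. This stands: case 1 is a permission set against a prohibition. Case 4 has no such way out, because one row says discontinue and the other directs a reduced dose.

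**A causality work-up is required in any event.** Section 6.2.2.1 calls for one whichever row is consulted, so the Grade 3 row does not operate without it. This also stands, but Section 6.2.2.1 does not link the result to resuming or stopping, and the 7-day rule still applies as written.

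**Case 4 may have an implied answer.** Table 6-2 is titled as covering adverse drug reactions, and Section 6.2.1 ties NIR178 changes to treatment-related events. Once another cause is found, one could argue that the Grade 3 row no longer governs. That is a reasonable reading, but the documents do not state it.

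**Practical weight is limited.** SAP Section 4 says the study is closed out for insufficient efficacy, so an amendment would have little prospective use. Deviations are still to be tabulated and listed, so a stated basis for classifying them remains useful.

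**Conclusion.** The inconsistency holds for patients with normal baseline ALT, AST and bilirubin and no cholestasis. Two of four cases give contrary directions. Case 4 is the firm conflict, most clearly between day 8 and day 14; case 1 is the weaker one. A third case agrees in direction but differs on the resolution level and on medical monitor discussion. This rests on reading the listed combined pattern as a trigger of the Grade 3 row. Its place between the Grade 2 and Grade 4 rows, with one complete instruction, makes a text-extraction fault an unlikely explanation.

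Three stronger readings are not supported:

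- A reader might infer that every patient with the pattern falls under both rows. The baseline and cholestasis conditions rule that out.
- A reader might take the related-event rates in Protocol Section 2.3 (AST increase 20/165 = 12.1%, ALT increase 16/165 = 9.7%) as the frequency. Those are all-grade events with no bilirubin criterion. The documents do not give the frequency of the combined pattern, and the Amendment 6 rationale reports no Hy's law cases to date.
- A reader might infer that one row lets dosing continue through the event. Neither does, since both start with a hold.

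**What to change.** The sponsor must reconcile the Grade 3 AST/ALT row and the combined-elevations row of Table 6-2, and align both with Section 6.2.2.1. The pattern should appear once, or with a stated precedence, and have one action and one resolution condition. The same edit should settle whether the cholestasis condition applies throughout, whether medical monitor discussion is required, and that the dose-level reduction refers to NIR178. No view is taken here on which rule is right.

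The cost is a table edit in an amendment or a clarification letter. With the study closing, the minimum is a short documented statement, before deviations are finalised, of which row was used to classify any affected case. No analysis, sample size or decision threshold changes.

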6.2.2.1 Follow up on potential drug-induced liver injury (DILI) cases

Patients with transaminase increase combined with total bilirubin increase may be indicative of potentially severe DILI, and should be considered as clinically important events and assessed appropriately to establish the diagnosis. The required clinical information, as detailed below, should be sought to obtain the medical diagnosis of the most likely cause of the observed laboratory abnormalities.

The threshold for potential DILI may depend on the patient's baseline AST/ALT and total bilirubin value; patients meeting any of the following criteria will require further follow-up as outlined below:

- For patients with normal ALT and AST and total bilirubin value at baseline: AST or ALT > 3.0 x ULN combined with total bilirubin > 2.0 x ULN
- For patients with elevated AST or ALT or total bilirubin value at baseline: [AST or ALT > 3.0 x baseline] OR [ALT or AST > 8.0 x ULN], whichever occurs first, combined with [total bilirubin > 2.0 x baseline AND > 2.0 x ULN]

As DILI is essentially a diagnosis of exclusion, other causes of abnormal liver tests should be considered and their role clarified before DILI is assumed as the cause of liver injury.

A detailed history, including relevant information such as review of ethanol consumption, concomitant medications, herbal remedies, supplement consumption, history of any pre-existing liver conditions or risk factors, should be collected.

Laboratory tests should include ALT, AST, total bilirubin, direct and indirect bilirubin, GGT, GLDH, prothrombin time (PT)/INR, alkaline phosphatase, albumin, and creatine kinase.

Evaluate status of liver metastasis (new or exacerbation) or vascular occlusion – e.g. using CT, MRI, or duplex sonography.

Perform relevant examinations (Ultrasound or MRI, ERCP) as appropriate, to rule out an extrahepatic cause of cholestasis. Cholestasis (is defined as an ALP elevation > 2.0 x ULN with R value < 2 in patients without bone metastasis, or elevation of the liver-specific ALP isoenzyme in patients with bone metastasis).

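### Two rows of Table 6-2 share the trigger ALT/AST above 3×ULN with bilirubin above 2×ULN but prescribe different actions, and the combined-elevation row lacks the elevated-baseline heading used in 6.2.2.1

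*Protocol*

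**What the plan says.** **Grade 3 AST/ALT row (Table 6-2).** Besides Grade 3 enzyme values, the row lists "ALT or AST >3 x ULN and TBL >2 x ULN (or international normalized ratio [INR] >1.5". Treatment is held. If values recover within 7 days, the site may "consider resuming PDR001 at the same dose and NIR178 at a lower dose after discussion with the Novartis Medical Monitor". After that, "close monitoring with at least weekly LFTs is recommended for 1 cycle of treatment. Otherwise, discontinue study treatment". The row does not mention DILI adjudication.

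**Combined-elevation row (Table 6-2).** The criterion opens "For participants with normal baseline ALT and AST and total bilirubin value: AST or ALT >3.0 x ULN", together with bilirubin above 2×ULN. It continues "without evidence of cholestasis OR [AST or ALT >3x baseline OR > 8.0 xULN], whichever is lower, combined with" bilirubin above both 2×baseline and 2×ULN. Interruption and DILI adjudication are marked mandatory. Two outcomes follow: "If causality assessment indicates that DILI is probable: Permanently discontinue participant from treatment", or "If not DILI: Treat the identified cause according to institutional guidelines. Once resolved, reduce by one dose level". This row sets no 7-day limit.

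**Section 6.2.2.1.** The same two criteria appear here, each with its own population. The second begins "For patients with elevated AST or ALT or total bilirubin value at baseline: [AST or ALT > 3.0 x baseline".

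**Status of the table.** Its introduction makes its instructions the basis for calling a protocol deviation. The text of 6.2.1 adds that permanent discontinuation is mandatory where the table indicates it. A patient with clinical benefit may nevertheless continue after documented discussion with the sponsor.

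**The concern.** A dose-modification table should give a site one answer for one event. Here a patient can satisfy two rows whose later steps differ, and the document does not say which row governs. Because the table defines deviations, a site that follows one row can be counted as deviating from the other. SAP section 2.3.2 tabulates deviations by category, so the ambiguity reaches the report.

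The missing heading is a second, separate gap. If the normal-baseline heading is taken to cover the whole cell, patients who entered with raised liver tests have no stated route into the mandatory DILI adjudication. Such patients are eligible: exclusion criterion 14 (section 5.3) removes only those with AST or ALT above 3×ULN or bilirubin above 1.5×ULN.

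**Working it through.** The plan gives no figure to reproduce. The check is a comparison of texts with simple threshold arithmetic.

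**1. Can one event meet both rows?** The first criterion of the combined row and the bilirubin trigger of the Grade 3 row use the same cut-offs: 3×ULN for ALT/AST and 2×ULN for bilirubin. Take an illustrative patient (assumed values) with normal baseline AST, ALT 0.8×ULN and bilirubin 0.6×ULN. ALT rises to 4.0×ULN and bilirubin to 2.3×ULN without cholestasis. Since 4.0 > 3.0 and 2.3 > 2.0, both rows are met. If the lines of the Grade 3 cell were instead read as cumulative, a Grade 3 enzyme rise with bilirubin above 2×ULN would still meet both.

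**2. What does each row then require?** Assume both clocks start at the hold and both rows treat the same day as recovery. The second assumption is a simplification: the Grade 3 row asks for Grade 1 or baseline, while the combined row monitors to the ULN or baseline.

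| Situation | Grade 3 row | Combined row | One action satisfies both? |
|---|---|---|---|
| DILI probable, recovered by day 7 | resumption may be considered | permanent stop | Yes: stop |
| DILI probable, not recovered by day 7 | stop | permanent stop | Yes: stop |
| Not DILI, recovered by day 7 | may resume, NIR178 lower | one level lower | Yes: resume lower |
| Not DILI, recovered days 8 to 14 | stop | one level lower | **No** |

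The window closes at day 14 because 6.2.1 requires discontinuation for non-immune events that delay dosing longer than that, with exceptions. The third line agrees because 6.2.1 does not allow PDR001 to be reduced, so the reduction can only be in NIR178.

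**3. Does any text rank the rows?**
- The word mandatory in the combined row attaches to interruption and adjudication, which are compatible with the Grade 3 row's hold. The conflict arises later, at the choice between resuming and stopping.
- The table's general note on basing changes on the worst toxicity so far does not help, because this is one toxicity under two rows.
- The clinical-benefit exception in 6.2.1 is a case-by-case route and does not set an order.

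**4. The heading.** Three readings of the second criterion are possible:
- *The normal-baseline heading covers it.* Elevated-baseline patients then have no stated entry to the row.
- *It belongs to elevated-baseline patients, as in 6.2.2.1.* The row then works as intended.
- *It is open to everyone.* Its ALT/AST trigger is min(3 × baseline, 8×ULN). An assumed baseline of 0.5×ULN gives 1.5×ULN, 0.8 gives 2.4×ULN, and 1.0 gives 3.0×ULN. Normal-baseline patients could then enter below 3×ULN.

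The content of the criterion favours the second reading, but the printed cell does not say so.

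**The case against.** The best reply is that 6.2.1 already settles the matter: permanent discontinuation is mandatory wherever the table indicates it, so a stop in either row binds. This disposes of the probable-DILI situations. A reader might infer that the Grade 3 row permits rechallenge of a patient with probable DILI. The documents do not support that. The row only allows resumption to be considered, after discussion with the medical monitor, while the combined row's adjudication and permanent stop apply at the same time. Stopping complies with both.

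For the patient without DILI who recovers on days 8 to 14, the same rule leans toward the Grade 3 row's stop. It does not say that the combined row's instruction yields, and that instruction is written specifically for a patient whose DILI work-up is negative. This part of the point stands.

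Two other strong readings fail:
- A reader might infer that the second criterion swallows the first and empties the cholestasis exclusion. That follows only if the criterion is open to everyone. On the 6.2.2.1 reading, normal-baseline patients stay at 3×ULN and the exclusion works.
- A reader might infer that everyone with a raised enzyme at baseline who meets the second criterion also meets the Grade 3 row's bilirubin trigger. Counter-example: baseline AST 1.5, ALT 0.5 and bilirubin 0.8×ULN; now AST 1.6, ALT 1.6 and bilirubin 2.3×ULN. ALT 1.6 > 3 × 0.5 = 1.5, and bilirubin 2.3 exceeds both 2 × 0.8 = 1.6 and 2.0. The second criterion is met, yet neither enzyme exceeds 3×ULN.

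It is also fair to say that the heading may simply have been lost when the PDF was read. The row conflict does not depend on it.

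**Conclusion.** The point holds as a minor drafting fault in a safety table, and it rests mainly on the unranked rows. There is one direct conflict, in patients judged not to have DILI who recover on days 8 to 14. There is also one loose end: the Grade 3 row, read alone, does not send the site to DILI adjudication before resumption is considered. The heading gap is real against 6.2.2.1 as the text is printed, subject to the extraction caveat.

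The documents do not support calling this an unprotected hazard. The Grade 3 row holds treatment at its trigger whatever the baseline, and 6.2.2.1 requires work-up of elevated-baseline patients in its own right and SAE reporting of DILI cases. Section 2.3 describes transaminase rises as generally reversible and manageable. The Amendment 6 rationale reports no Hy's law cases and no hepatic deaths to that date. SAP section 4 says the study is closed out. No efficacy endpoint or analysis is affected. How many patients fell into the conflicting situation cannot be told from the documents.

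**What to change.** In Table 6-2:

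1. Before the second criterion of the combined row, insert a heading for participants with elevated baseline AST, ALT or total bilirubin, matching 6.2.2.1.
2. State that the combined row takes precedence over the Grade 3 AST/ALT row when both are met, so that no rechallenge occurs before DILI has been adjudicated.
3. Say whether the 7-day recovery limit still applies once DILI is excluded.

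The cost is one heading and one or two sentences, with no added tests or visits. The downside is that resumption may be delayed in some patients until adjudication is complete. With the study closed out, the practical use is for any patients still on treatment and for classifying deviations consistently in the report. Section 4.3 foresees roll-over protocols but does not say that they would reuse this table.
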